Objectives of this project are to evaluate the feasibility of constructing a concurrent external control for the recifercept phase 2 clinical trial (Study C4181005) using achondroplasia patients from the ongoing prospective natural history study (Study C4181001) and to compare selected outcomes of interest such as height growth, achondroplasia-related complications, patient functional status, and quality of life between achondroplasia patients in Study C4181005 and those in the concurrent external control. Ultimately, this project will assess the feasibility of leveraging the ongoing Study 4181001 to construct a concurrent external control for the recifercept pivotal trial.

Research question and objectives

There are two research questions:

1) Can a concurrent external control for the recifercept phase 2 clinical trial be constructed using achondroplasia patients from a prospective observational natural history study?

2) What are differences in height growth, achondroplasia-related complications, patient functional status, and quality of life between patients enrolled in the recifercept phase 2 clinical trial and those in the concurrent external control?

Objectives of this pilot project will be:

- 1. Construct a concurrent external control arm for recifercept phase 2 clincial trial using achondroplasia patients from a prospective observal natural history study
- 2. If objective #1 is met, the following will be compared to examine differences between patients enrolled in the recifercept phase 2 clincial trial and those in the concurrent external control:
 - Height growth
 - Selected anthropometric measurements, including but not limited to: standing height, sitting height, knee height, arm span, length of the legs, sitting height/standing height ratio, arm span to height/length difference, knee height/lower segment ratio

PFIZER CONFIDENTIAL

- Achondroplasia-related orthopaedic complications (including lordosis, kyphosis, small foramen magnum, spinal stenosis), and other achondroplasia-related complications (including apnea, AOM, and hydrocephalus)
- Differences in functional status and health-related quality of life

Study design

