9.6. Data analysis

A single pooled dataset will be released for analysis. The release will occur when for selected, targeted data (in Table 3): a) review and documentation of relevant CRF and non-CRF data; and b) all open queries are resolved. There will be two releases of data. The first release coincides with approximately 30 pairs of patients – that is, a patient from C4181001 matched to a patient from C4181005 – having 6 months of growth data. The second release will take place at the beginning of the interim analysis for C4181005. There may be an additional release of data from both studies that coincides with the completion of C4181005.

Descriptive statistics will be tabulated on patient demographic and baseline clinical characteristics between achondroplasia patients from Study C4181005 and patients from Study C4181001 who meet all the inclusion and exclusion criteria of Study C4181005. To construct a concurrent external control for Study C4181005, a propensity score (PS) will be created to achieve balance across covariates between achondroplasia patients from Study C4181005 and patients from Study C4181001 who meet all the eligibility criteria of Study C4181005. The PS will be estimated using standard logistic regression approaches with the "outcome" variable being the data source (whether patients were included in Study C4181005 and exposure to recifercept treatment) and the predictors being the variables associated with both the exposure (recifercept treatment) and the outcomes of interest (i.e. height growth). This model will provide the predicted probability of being in the trial cohort relative to the concurrent external control cohort as a function of the covariates (the propensity score of being included in Study C4181005). The potential covariates may include demographics (e.g. age, gender, race and ethnicity), clinical characteristics (e.g. presence of achondraplasia-related complications, Tanner stage, and other nonachondroplasia-related conditions of medical significance). The distribution of the PS will be reviewed and patients with a PS in the areas of nonoverlap and/or with extreme PS values might be excluded to improve validity (PS trimming). Each patient in the PS trimmed receifercept group will be matched on a ratio of 1:1 with patients in the PS trimmed concurrent external control using optimal nearest neighbour matching with a maximum

PFIZER CONFIDENTIAL

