CT24-WI-GL03-RF03 2.0 Non-Interventional Statistical Analysis Plan For Secondary Data Collection Study 01-Jun-2020 Page 11 of 17 related conditions of medical significance). The distribution of the PS will be reviewed and patients with a PS in the areas of nonoverlap and/or with extreme PS values might be excluded to improve validity (PS trimming). Each patient in the PS trimmed receifercept group will be matched on a ratio of 1:1 with patients in the PS trimmed concurrent external control using optimal nearest neighbour matching with a maximum caliper of 1%. Pre- and post-matching balance will be assessed using standardized differences between these two PS-matched groups. A negative control outcome may also be identified to evaluate the pre- and post-matching balance. There are different options that will be considered while modelling via PS. These include:

- 1. Calipers: range from [.01,.25]
- 2. Statistic (used to match treated to control subject): logit of PS, minimizing difference of PS, Mahalanobis distance
- 3. Ratio match (treatment-to-untreated): 1-to-1, 1-to-m

Exact matching can be included within the PS model. Exact matching will be done by gender. A binary variable will be created to specify race. The variable will have the value of "Yes" for "White" and "No" for all other values.

Standardized mean differences of the matched variables are the main criteria used to determine whether objective 1 is met. An external control dataset is confirmed (i.e., objective 1 is met) when all of the standard mean differences for the matched variables are less than 0.1.

After the concurrent external control is constructed by PS matching, descriptive statistics will be tabulated on patient demographic and baseline clinical characteristics between achondroplasia patients from PS-matched recifercept phase 2 trial cohort and those from PS-matched concurrent external control. Two-sample T-tests will be used for continuous variables, and chi-square tests for categorical variables assuming the distribution is normal. Frequency of primary, secondary and exploretary outcomes of interest and 95% confidence intervals will be computed.

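### The Objective 1 rule looks only at balance among matched children, so with poor age overlap it can certify a control for a minority of the trial

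*SAP*

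**What the plan says.** SAP 7.2.1 introduces the criterion with "Standardized mean differences of the matched variables are the main criteria used to determine whether objective 1 is met" and then turns it into a sufficient condition: "An external control dataset is confirmed (i.e., objective 1 is met) when all of the standard mean differences for the matched variables are less than" the limit of 0.1. No other criterion is named there, in the summary table of SAP 7.2.4, or in the protocol.

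The set on which the differences are computed is left open:
- Trimming is optional and has no threshold: "patients with a PS in the areas of nonoverlap and/or with extreme PS values might be excluded to improve validity (PS trimming").
- The base text matches 1:1 "using optimal nearest neighbour matching with a maximum caliper of 1"%, without saying on which scale.
- The option list then gives "Calipers: range from [.01,.25"], three matching statistics, and 1-to-1 or 1-to-m ratios. It sets no order or selection rule.
- SAP 7.2.2 requires a 1:1 set for Objective 2 if the matching route is used.
- The code in SAP 10.3 writes no caliper, uses variable-ratio matching with `kmax = 4`, models sex, age and White, and matches exactly on sex and White. The text of 7.2.1 commits to exact matching on gender only.

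The protocol abstract gives the purpose: "Ultimately, this project will assess the feasibility of leveraging the ongoing Study 4181001 to construct a concurrent external control for the recifercept pivotal trial".

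**The concern.** A trial child without a match drops out of the calculation and never counts against the verdict. The rule therefore cannot tell 60 of 63 matched from 6 of 63. Yet the first research question is whether a control can be built for the phase 2 trial, and a pass opens Objective 2.

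If overlap is poor, the pass would describe a selected subset of the trial, and the Objective 2 estimate would apply to that subset with much less precision. SAP section 1 places the amendment after last subject, last visit, so the unordered options could be tried with all data collected.

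**Working it through.** **Inputs from the documents.** Treated children: about 63 (SAP 2.1), fewer if some did not complete Visits 1 through 11. Controls: about 300 anticipated. All trial patients come from C4181001 (SAP 2) and no patient is in both datasets (SAP 2.1), so at most 300 − 63 = 237 before eligibility screening. Propensity model: sex, age, White (SAP 10.3). Pass rule: all standardized mean differences (SMDs) below 0.1.

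**Assumed, because the documents do not give them.** Age and race distributions, and the number of eligible controls (80, 150 or 237 used).

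**Is there a retention condition elsewhere?** The rule has no accompanying figure to reproduce, so the candidate safeguards were checked in turn.
- Protocol Table 1 gives pair counts, but Protocol 9.4 limits study size to the second objective. At type I error .05 and power .8 the counts run from 88 down to 3 according to the assumed ratio, so they set no single floor.
- Protocol 9.6 says "The first release coincides with approximately 30 pairs of patients". That times a data release. It is 30/63 = 48% of the trial.
- Protocol 9.6 also plans further methods to keep more patients, with no threshold.
- The statement that each trimmed recifercept patient will be matched applies after trimming and within the caliper. It is not a pass condition.

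**Why balance can come almost free.** In a 1:1 set matched exactly on sex and White, both of those SMDs are 0 at any size, which leaves age. Within a sex-by-White cell the fitted logit is a + β × age. A pair within a caliper of c standard deviations of the logit therefore differs in age by at most c × SD(logit)/|β|. Under poor age overlap, age drives most of the spread, SD(logit) ≈ |β| × SD(age), and the age SMD (on the pre-match SD) is at most about c. A c well below 0.1 then passes however few pairs remain; c = .25 need not.

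**Simulation.** 63 treated, logistic propensity score, optimal 1:1 matching, exact on sex and White, caliper .01 on the propensity-score scale, 150 runs per cell (Monte Carlo standard error at most √(0.5 × 0.5/150) = 4 points). Each cell lists results for 80 / 150 / 237 controls.

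| Assumed age overlap | Median matched of 63 | Mean share matched | Rule passes | Passes with under half matched |
|---|---|---|---|---|
| Good | 55.5 / 63 / 63 | 86 / 98 / 100% | 99 / 100 / 100% | 1 / 0 / 0% |
| Moderate | 27.5 / 41 / 50 | 44 / 65 / 79% | 100 / 100 / 100% | 76 / 7 / 0% |
| Poor | 13 / 19 / 24 | 21 / 31 / 40% | 100 / 100 / 100% | 100 / 100 / 96% |

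A separate simulation with other assumed ages gave medians of 9 to 22 under poor overlap, passing in 100% of runs, and 59 to 63 under good overlap.

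**Sensitivity.**
- Exact on sex only, poor overlap, same caliper: medians 16 / 23 / 28, rule passes in 30 / 43 / 56%, passes with under half matched 30 / 41 / 45%.
- Caliper .01 read as SD of the logit (the code's distance is `lps`): mean share matched 27–54% good, 12–29% moderate, 8–19% poor; rule passes in 97–100%.
- Caliper .25 SD of the logit: 90–100%, 71–93% and 44–60% matched. Passes with under half matched appear only under poor overlap (3–89%).

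**What lost pairs cost.** For a plain two-group comparison at two-sided .05 and 80% power, detectable difference = (1.960 + 0.842) × √(2/n) SD. This gives 0.50 SD for n = 63, 0.70 for n = 32 and 1.25 for n = 10. Power for 0.5 SD is 80%, 52% and 20%. The SD of height Z-score is not given, and this ignores repeated measures.

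**The case against.** The case against has real force.

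- **Overlap may be good.** Trial children were recruited from C4181001 and the trial's criteria are applied to the controls. If so, on the propensity-score scale nearly all children match.
- **The adverse setting mixes text and code.** The 1:1 caliper comes from the text, and exact matching on White from the code. A reader might infer that tightening the caliper always buys balance, or that the rule nearly always says yes. The documents do not support that. With exact matching on sex only, one set of assumed ages with 80 mostly younger controls passed in 68% of runs at caliper .05 and 43% at .01, because fewer pairs leave more chance imbalance in White. If clinical covariates are added, as SAP 7.2.1 and 7.2.4 allow, passes become rare: 0–16% at any single caliper with five assumed comorbidities.
- **IPW (inverse probability weighting) discards nobody.** Its code uses `region = allobs`, so a discarded remnant is not an issue on that route, although no effective sample size is requested.
- **SMDs are only the main criteria.** That wording leaves room for others, but none is written.
- **No pivotal trial is at risk.** A reader might infer that one would be planned on a false result. Protocol section 5 records that recifercept was discontinued.

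These points limit how often the problem bites and what follows from it. They do not supply the missing condition.

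**Conclusion.** The decision rule is incomplete. Followed exactly, it can declare a control for Study C4181005 confirmed when only a minority of its children have a match. Under assumed poor age overlap, with the coded exact matches, 1:1 and a propensity-score-scale caliper of .01, medians of 9 to 24 of 63 matched went with a pass in essentially all runs. Under good overlap on that scale the problem does not arise. With sex-only exact matching it is less frequent but remains under poor overlap.

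The size rests on assumed ages and control counts, so it shows what the rule permits and does not predict the result. It also depends on the unstated caliper scale. Nothing in the documents shows that most trial children will go unmatched. Severity: should-fix.

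**What to change.** - Pre-specify one primary caliper with its scale, one primary distance and one primary ratio. Reconcile the code (no caliper, `kmax = 4`, exact on White) with the 1:1, 1%, gender-only text.
- Make Objective 1 conditional on all SMDs below 0.1 and on a minimum share of eligible C4181005 children matched, chosen and justified by the sponsor. As an example only, 80% of 63 is 50.4, so 51 children; the documents contain no source for that figure.
- For each option tried, report matched out of eligible and compare matched with unmatched treated children. For IPW, report the effective sample size per group.
- If balance is reached only below the minimum, report the control as built for a subset and not for the trial population.

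The cost is a few lines of SAP text and one table. The downside is that Objective 1 could be reported as not met where the present rule would pass it.

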2.2 STUDY OBJECTIVES

Objectives of this pilot project include:

1. Construct a concurrent external control arm for recifercept phase 2 clincial trial using achondroplasia patients from a prospective observal natural history study 2. If objective #1 is met, the following will be compared to examine differences between patients enrolled in the recifercept phase 2 clincial trial and those in the concurrent external control:

- Selected anthropometric measurements, including but not limited to: standing height, sitting height, knee height, arm span, length of the legs, sitting height/standing height ratio, arm span to height/length difference, knee height/lower segment ratio
- Achondroplasia-related orthopaedic complications (including lordosis, kyphosis, small foramen magnum, spinal stenosis), and other achondroplasiarelated complications (including apnea, AOM, and hydrocephalus)
- Differences in functional status and health-related quality of life

PFIZER CONFIDENTIAL

CT24-WI-GL03-RF03 2.0 Non-Interventional Statistical Analysis Plan For Secondary Data Collection Study 01-Jun-2020 Page 8 of 17

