3 HYPOTHESES AND DECISION RULES

3.1 STATISTICAL HYPOTHESES

This study includes an CCL element and specific hypotheses to be tested. That null hypothesis is limited to a comparison of height Z-Score. The null hypothesis for that objective is as follows:

Null: Mean Change from Baseline of Height Z-Score up to 12 months is no different between patients on treatment and patients in the natural history study.

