3.2 STATISTICAL DECISION RULES

The alpha level will be 0.05, 2-sided. No adjustments for multiple comparisons will be made.

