Another method to construct an external control for C4181005 for the purpose of estimating the Average Treatment Effect (ATE) of recifercept is Inverse Probability Weights (IPW). IPW will use PS to weight the observations prior to the analysis of height growth. Weights are calculated for each subject as 1/PS for Recifercept and 1/(1-PS) for the untreated group. Standardized differences between the untreated and Recifercept groups will be assessed both before and after weighting. Standardized mean differences of <10% may be considered a negligible difference.

7.2.2 Objective 2

Achondroplasia disease measures including height growth, anthropometric measurements, difference in functional status and health-related of life will be summarized using descriptive statistics.

Analyses of Height Z-Score and Arm-Span-to-Height Difference

If objective 1 is met, either a matched dataset – exclusively with a ratio of treated to untreated of 1:1 - via PS or a dataset augmented by IPW will be used to analyze height Z-Score. Baseline summaries of Height Z-score and Arm-Span to Height-difference and change from baseline a months 3, 6, 9, and 12 will be presented.

7.2.3 Safety Analyses

Not applicable.

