10.3 APPENDIX 3: DIAGNOSIS AND PROCEDURE CODES USED IN THE STUDY

Propensity Score Matching

proc psmatch data = adsl ;

class SEX DRUG WHITE ;

psmodel DRUG (treated = 'Recifercept') = SEX AAGE WHITE ;

match method = varratio (kmax = 4) distance = lps exact = (SEX WHITE);

assess lps allcov / weight = none plots = (barchart boxplot);

```
output out(obs = match) = outasa lps = _Lps matchid = _MatchID ;
```

run;

PFIZER CONFIDENTIAL

CT24-WI-GL03-RF03 2.0 Non-Interventional Statistical Analysis Plan For Secondary Data Collection Study 01-Jun-2020 Page 16 of 17

MMRM with Propensity Score Matching clusters

```
proc mixed data = ps_match_mmrm ;
    by paramcd ;
    class _MatchID usubjid sex drug (ref = 'Not Treated') ;
    model chg = month drug / s ; /*** s = Solution for Fixed Effects ***/
    random int month / subject = usubjid(_MatchId) ;
run ;
```

Inverse Probability Weighting

```
proc psmatch data = adsl region = allobs ;
    class SEX DRUG WHITE ;
    psmodel DRUG (treated = 'Recifercept') = SEX AAGE WHITE ;
    assess lps var = (SEX AAGE WHITE) / weight = atewgt plots = (barchart boxplot) ;
    output out(obs = all) = ipw_ate ATEWGT = _ATE_ ;
```

run;

MMRM with Inverse Probability Weights

```
PROC GLIMMIX DATA = ate_ipw METHOD = quadrature (qpoints = 27) EMPIRICAL =
classical NOREML ;
NLOPTIONS GCONV = 1E-10 TECHNIQUE = TRUREG ;
where PARAMCD APSBLFL = "Y" ;
CLASS DRUG (REF = "Not Treated") USUBJID ;
MODEL CHG = DRUG MONTH / SOLUTION ;
RANDOM INT MONTH / subject = USUBJID WEIGHT = _ATE_ ;
```

RUN;

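### The one height Z-score test may use either a 1:1 matched set or an ATE-weighted set, with no primary named and no selection rule, so the estimand is not fixed and the 5% level is not protected

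*SAP*

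**What the plan says.** - **Aim.** SAP 2.2, objective 1: "Construct a concurrent external control arm for recifercept phase 2 clincial trial".
- **Hypothesis.** SAP 3.1 states one null only: treated and natural-history children do not differ in their average height Z-score change over a period of up to 12 months.
- **Level.** SAP 3.2: "The alpha level will be 0.05, 2-sided. No adjustments for multiple comparisons will be made".
- **Dataset for the test.** SAP 7.2.2 offers a matched dataset, restricted to 1:1, "via PS or a dataset augmented by IPW will be used to analyze height Z-Score". The model paragraph in 7.2 and the table in 7.2.4 repeat the alternative without ranking the two.
- **Weights.** SAP 7.2.1 declares the ATE as the target of weighting: "Weights are calculated for each subject as 1/PS for Recifercept and 1/(1-PS) for the untreated group". The code in 10.3 agrees ("assess lps var = (SEX AAGE WHITE) / weight = atewgt") and keeps all observations (`region = allobs`).
- **Matching.** SAP 7.2.1 starts from recifercept patients left after propensity-score trimming and seeks a control for each. It lists calipers from 0.01 to 0.25, three match statistics, and ratios of 1-to-1 or 1-to-m. The code in 10.3 uses `varratio (kmax = 4)`, and its MATCH statement names no caliper.
- **Gate.** Objective 1 is met when every standardized mean difference of the matched variables is below 0.1. A 10% threshold is also mentioned after weighting.
- **Order in the protocol.** Section 9.6 describes matching first and weighting as a further option.

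**The concern.** One hypothesis has two admissible analyses that answer different questions. Matching asks what recifercept did in the trial children for whom a counterpart exists. ATE weighting also reweights the trial children, by 1/PS, towards the pooled eligible population, which fits poorly with an objective of building a control arm for the phase 2 trial. If the effect varies with age, the two differ in expectation.

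The choice is also open at the point of analysis. The balance gate does not settle it, because both datasets can pass. SAP section 1 places the current amendment after last subject, last visit, and 10.3 supplies code for both routes. Nothing forbids running both and reporting the more favourable. The project exists to judge whether this control method is usable, so an unfixed estimand weakens its main product.

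**Working it through.** **1. The plan's own figure.** One pre-specified two-sided test at 0.05 has type I error 0.05. That holds for either method if it is fixed in advance and its standard error is valid.

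**2. Both run, either significant result used.** The SAP does not state this rule; it is the case left unprevented. For independent tests: 1 − (1 − 0.05)² = 1 − 0.9025 = 0.0975. For correlated tests, under a bivariate normal null, P(|Z₁| > 1.96 or |Z₂| > 1.96):

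| Correlation | Type I error |
|---|---|
| 0 | 9.75% |
| 0.5 | 9.1% |
| 0.7 | 8.4% |
| 0.8 | 7.8% |
| 0.9 | 7.0% |
| 1 | 5.0% |

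To locate the correlation, null data were simulated with 63 treated (SAP 2.1), 100 or 237 controls, and trial-versus-control age shifts of 0.3 or 0.6 SD. Matching was optimal 1:1, exact on sex, caliper 0.25 SD of the logit score; 4,000 datasets per setting. All inputs except the 63 are assumptions.

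- Correlation of the two test statistics: 0.71–0.87.
- Either-test rejection: 8.2–9.5%.
- Matching alone: 4.5–5.1%. Weighting alone: 5.6–6.4%, so part of the excess is the weighted test's own size, not selection.

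**3. Choice on balance only.** Standardized differences use no outcome data, so selecting on them adds no inflation.

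**4. Whose effect the ATE is.** Natural-history share = n₀ / (n₀ + 63). About 300 patients are anticipated, the pooled datasets share no patients, and trial patients are said to come from the natural history study. The upper bound is thus 300 − 63 = 237, before the eligibility criteria in SAP 4.1. The eligible number is not given.

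| Eligible controls (assumed) | Share |
|---|---|
| 50 | 50/113 = 44% |
| 63 | 63/126 = 50% |
| 100 | 100/163 = 61% |
| 150 | 150/213 = 70% |
| 237 | 237/300 = 79% |

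**5. How far the estimands can part.** Assume an effect of 0.3 per SD of age (zero at the control mean) and trial children 0.6 SD older.

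- Effect in all treated: 0.3 × 0.6 = 0.18.
- ATE, 100 controls: 0.18 × 63/163 = 0.07.
- ATE, 237 controls: 0.18 × 63/300 = 0.04.
- Mean matched estimate: 0.134 and 0.145. The caliper left about 53.6 and 60.3 pairs, so matching covers only part of the trial group.

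A second assumed scenario has 237 controls and an effect falling with age from 1.0 SD to 0. Matching gives 0.44 against an ATE estimate of 0.52 for a 1.5-year mean age difference, and 0.36 against 0.50 for 2.5 years. ATT weights give 0.42 and 0.33, close to matching. The direction of the gap depends on the assumed gradient.

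**6. Information kept on the treated.** With 237 controls, the effective treated number under ATE weights was 59, 50 and 37 of 63 for mean age differences of 0, 1.5 and 2.5 years.

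**The case against.** The wording offers one dataset or the other; it does not say that both tests will be run or that results will guide the choice. Objective 1 is an outcome-free gate, and a choice made there costs no type I error. This stands. A reader might infer that the 5% level is broken; the documents support only that it is not protected.

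A reader might also infer that the late amendment introduced the choice. The change list does not say so, and protocol 9.6 already allowed weighting. The timing shows only that the choice is still open late.

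A third tempting reading is that the ATE population is mostly natural-history children. That needs more than 63 eligible controls, and the documents give no count. Controls must meet the trial's criteria and come from the same source study, which narrows the contrast. Nor is the matched set the trial population, since trimming and the caliper can drop treated children.

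The ATE is openly declared, and the protocol's reason for additional methods is to keep more patients, whereas 1:1 matching discards controls. That is a fair case for a weighted analysis in a stated role, but not for leaving the roles unstated.

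Finally, the simulations use simpler tests than the SAP's repeated-measures model, and the age differences and effect gradients are invented. They show possible size, not a forecast. This is also a feasibility pilot for a discontinued product.

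**Conclusion.** The point holds in a limited form. One null at two-sided 0.05 has two admissible analyses with different target populations, no primary and no selection rule. Two consequences follow.

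- **Estimand.** It is not fixed. The results differ in expectation only if the effect varies with characteristics on which the groups differ; the size depends on assumptions the documents do not settle.
- **Error rate.** It is not protected. Inflation to about 7–8% (correlation 0.8–0.9), or 9.75% for independent tests, requires that both be run and results steer the choice. It is nil if the choice rests on balance alone.

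The natural-history share (44% to 79% for 50 to 237 controls) and the loss of treated information are likewise conditional. The matter should be corrected, but given the pilot status it does not invalidate the study.

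**What to change.** Before any outcome analysis:

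1. In SAP 7.2.2 and 7.2.4, name the 1:1 matched analysis as the single primary test of the height Z-score null.
2. In 7.2.1, fix one caliper and one match statistic, chosen on balance without sight of outcomes. Otherwise the primary still has open forks.
3. In 10.3, change the matching code from `varratio (kmax = 4)` to 1:1, to agree with 7.2.2, and write the chosen caliper into it.
4. Label the weighted analysis as sensitivity and use ATT weights in 7.2.1 and in the ASSESS, OUTPUT and model code: 1 for recifercept, PS/(1 − PS) for untreated. Apply them on the same trimmed propensity-score region as the matching. Both analyses then target approximately the treated trial children.
5. Keep the ATE version as supplementary if wanted.

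The cost is a few sentences and code options. The primary and sensitivity results would no longer generalise to the whole eligible natural-history population, and 1:1 matching discards some controls.
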